# Protocol & ICF (GXMU-PCa-AI-KY20260016)

## Document 1: Study Protocol

**Document Version:** V1.0

**Effective Date:** January 28, 2026

**Unique Protocol ID:** GXMU-PCa-AI-KY20260016

**Official Study Title:** A Multicenter Study of a Deep Learning Model Based on Spatial Registration of Multimodal Imaging and Digital Pathology for Predicting Clinically Significant Prostate Cancer

**Brief Title:** Multimodal Imaging and Digital Pathology for Prostate Cancer Prediction

**Study Type:** Observational, prospective and retrospective multicenter cohort study

**Sponsor:** Guangxi Medical University

**Principal Investigator:** [name], Professor, Doctoral Tutor of Medical Science, Guangxi Medical University

**Ethics Approval Number:** KY20260016

**Ethics Committee:** Medical Ethics Committee of Guangxi Medical University

**Study Start Date:** May 30, 2025

**Primary Completion Date:** June 30, 2030

**Full Study Completion Date:** December 31, 2030

**Estimated Enrollment:** 3000 participants

**Study Status:** Recruiting

**Target Follow-up Duration:** 12 years

## 1. STUDY BACKGROUND AND RATIONALE

Prostate cancer is one of the most common malignant tumors in elderly males globally. Clinically significant prostate cancer (csPCa) is closely correlated with tumor progression, distant metastasis and cancer-related mortality. Accurate preoperative identification and risk stratification of csPCa remain major clinical challenges.

Multiparametric magnetic resonance imaging (mpMRI) and transrectal ultrasound (TRUS) are standard preoperative imaging modalities for patients with suspected prostate cancer. The PI-RADS v2.1 scoring system is widely adopted for lesion risk evaluation in clinical practice. Nevertheless, conventional imaging assessment fails

to fully reflect microscopic pathological heterogeneity, thereby resulting in frequent unnecessary prostate biopsies, inconsistent diagnostic accuracy, and potential overdiagnosis or underdiagnosis.

Digital whole-slide images (WSI) of pathological specimens provide high-resolution microscopic pathological features and serve as the diagnostic gold standard for prostate cancer. Spatial inconsistency between macroscopic imaging lesions and microscopic pathological changes restricts precise correlation of imaging manifestations with pathological grading results.

Artificial intelligence and deep learning techniques support high-throughput feature extraction and multimodal data fusion. Spatial registration algorithms enable accurate alignment between preoperative imaging lesions and postoperative microscopic pathological structures, which facilitates the construction of precise and interpretable diagnostic models for prostate cancer.

This multicenter observational study is designed to establish and validate a multimodal deep learning prediction model based on spatial registration of mpMRI, TRUS and digital pathological WSI. The model is intended to achieve non-invasive and accurate prediction of csPCa, standardize non-invasive risk stratification, reduce unnecessary prostate biopsy procedures, and provide evidence for optimizing clinical diagnostic and therapeutic decision-making.

## 2. STUDY OBJECTIVES

**Primary Objective:** To construct and validate a transformer-based multimodal deep learning model for the prediction of clinically significant prostate cancer using spatially registered multimodal imaging and digital pathology data. The area under the receiver operating characteristic curve (AUC) is applied to evaluate the diagnostic discriminative ability of the model.

**Secondary Objectives:** (1) To analyze the spatial correlation between macroscopic imaging characteristics and microscopic pathological heterogeneity of prostate lesions; (2) To validate the generalization performance of the model through internal cross-validation, external multicenter independent validation and international public dataset validation; (3) To evaluate the clinical application value and net clinical benefit of the model via decision curve analysis and clinical impact curve analysis; (4) To verify the clinical value of the model in optimizing prostate biopsy strategies, reducing unnecessary puncture and overtreatment, and improving early precise diagnosis and risk stratification of prostate cancer.

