## 3. STUDY DESIGN

This is a prospective and retrospective multicenter observational cohort study. No additional clinical interventions, experimental drugs or medical devices are applied to enrolled participants. Only routine standard-of-care clinical data, imaging data and pathological data are collected and analyzed.

The study population consists of two cohorts: a retrospective historical cohort and a

prospective newly enrolled cohort. All eligible participants receive standardized preoperative mpMRI and TRUS examinations, followed by clinically indicated prostate biopsy or radical prostatectomy with definitive pathological diagnosis.

All collected high-quality multicenter data are applied for model construction, spatial registration, multimodal feature fusion, model training, internal cross-validation and external multicenter independent validation.

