## 6. MODEL CONSTRUCTION AND VALIDATION

Biomechanically constrained non-rigid spatial registration technology is adopted to achieve precise spatial alignment between preoperative multimodal imaging lesions and postoperative digital pathological WSI. A transformer-based multimodal deep learning fusion model is constructed to explore potential correlations between macroscopic imaging manifestations and microscopic pathological heterogeneity, so as to establish an interpretable artificial intelligence prediction framework for csPCa.

Comprehensive model validation is performed through internal cross-validation, external multicenter independent validation and international public dataset verification. AUC is used as the primary indicator to evaluate model diagnostic performance. Decision curve analysis and clinical impact curve analysis are conducted to assess clinical practicability and net benefit of the model for clinical decision-making.

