## 7. OUTCOME MEASURES

**Primary Outcome Measure:** AUC of the multimodal deep learning model for predicting clinically significant prostate cancer at the time of baseline imaging and pathological data collection.

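### As worded, the plan lets pathology slides be both model input and source of the outcome label, so the primary AUC could be circular and unable to support its non-invasive, pre-biopsy aim

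*Protocol*

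**What the plan says.** **Data the model uses.** The primary objective in Section 2 is "prediction of clinically significant prostate cancer using spatially registered multimodal imaging and digital pathology data", with AUC as the measure of discrimination. Section 1 describes a "multimodal deep learning prediction model based on spatial registration of mpMRI, TRUS and digital pathological WSI". The brief title is "Multimodal Imaging and Digital Pathology for Prostate Cancer Prediction". Section 3 says that all the collected data "are applied for model construction, spatial registration, multimodal feature fusion, model training, internal cross-validation and external multicenter independent validation". Section 5 counts whole-slide images among the collected data.

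**Where the outcome comes from.** Section 1 says that slides "serve as the diagnostic gold standard for prostate cancer". Section 5 collects the slides together with their Gleason and ISUP results. No other pathological grade appears in the protocol, and no threshold for csPCa is given.

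**What the model is for.** Section 1: "The model is intended to achieve non-invasive and accurate prediction of csPCa". Sections 1 and 2 also want it to cut avoidable biopsies and improve biopsy strategy.

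**The primary outcome.** Section 7 names the AUC of the multimodal model, timed "at the time of baseline imaging and pathological data collection". It lists no inputs. Section 6 describes "precise spatial alignment between preoperative multimodal imaging lesions and postoperative digital pathological WSI" and a transformer fusion model that relates imaging appearance to microscopic heterogeneity. It does not say what that model receives when it is evaluated.

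**The concern.** A slide exists only after tissue has been taken. A model that needs one cannot be run at the moment when it is supposed to help decide whether to take tissue. If the csPCa label is read from the slide and the slide is also a predictor, the reference standard sits inside the test being evaluated (incorporation bias). The AUC then mainly measures how well an algorithm re-grades slides, not how well MRI and ultrasound identify csPCa before biopsy.

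A milder version could arise through registration. If validation cases are registered to their slides, and the resulting lesion masks or coordinates are passed to the model, it is told where the pathologist found tumour.

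In either case a high AUC could be reported as support for non-invasive prediction. The decision-curve, clinical-impact and biopsy-reduction analyses of the same model would inherit the error.

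**Working it through.** The protocol states no AUC, target or precision, so there is no figure of its own to reproduce. The check is first textual, then illustrative.

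**Step 1: the text side by side.**

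| Question | Where | What it supports |
|---|---|---|
| What is prediction based on? | Section 2, brief title, Section 1 | Imaging and digital pathology together |
| Which data enter fusion, training and validation? | Section 3 | All collected data; slides not excepted |
| What is the reference standard? | Sections 1 and 5 | Slides and their Gleason/ISUP grades |
| When is the model to be used? | Sections 1 and 2 | Before biopsy, non-invasively |
| What are the inputs when the AUC is computed? | Sections 6 and 7 | Not stated |

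Rows 1 to 3 let the slide be predictor and label source at once. Row 4 cannot be met by a model that does this. Row 5 leaves the conflict unresolved.

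**Step 2: size if slides are an input at evaluation.** All AUCs here are assumptions. Take equal-variance binormal scores for imaging and slide, independent given disease status, combined optimally.

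- Separation of each score: d = √2 · Φ⁻¹(AUC)
- Fused AUC = Φ(√(d_img² + d_slide²)/√2) = Φ(√(z_img² + z_slide²)), where z = Φ⁻¹(AUC)

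For a slide AUC of 0.97, z_slide = 1.881 and z_slide² = 3.537:

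- Imaging 0.50: z = 0, fused Φ(1.881) = 0.970
- Imaging 0.70: z = 0.524, fused Φ(√(3.537 + 0.275)) = Φ(1.953) = 0.975
- Imaging 0.80: z = 0.842, fused Φ(√(3.537 + 0.708)) = Φ(2.060) = 0.980

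| Assumed slide AUC | Imaging 0.50 | Imaging 0.70 | Imaging 0.80 |
|---|---|---|---|
| 0.93 | 0.930 | 0.941 | 0.955 |
| 0.95 | 0.950 | 0.958 | 0.968 |
| 0.97 | 0.970 | 0.975 | 0.980 |
| 0.99 | 0.990 | 0.991 | 0.993 |

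With slide AUC 0.97, raising imaging from worthless (0.50) to 0.80 moves the reported result by 0.980 − 0.970 = 0.010.

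**Step 3: sensitivity to independence.** With within-class correlation ρ = 0.5, the combined d² is (d_img² + d_slide² − 2ρ·d_img·d_slide)/(1 − ρ²). For slide AUC 0.95 and imaging 0.70, 0.80 and 0.90, the fused AUC is 0.954, 0.950 and 0.958, against 0.958, 0.968 and 0.981 under independence. For imaging 0.50 it is 0.971, because an uninformative but correlated score helps to cancel noise. The slide still dominates.

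**Step 4: the other end of the range.** If slides serve only to register and label training cases, and validation cases reach the model without slide-derived information, the fused AUC does not apply. The reported AUC is then the imaging AUC, and inflation from this source is zero.

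**The case against.** The strongest reply is that the protocol never says slides are fed to the model when it is evaluated. The primary objective's wording can describe the data used to build the model, with imaging alone at prediction. That reading fits the non-invasive purpose in Section 1, the biopsy-sparing aim in Section 2 and the imaging–pathology correlation described in Section 6. Section 7 gives only a time frame. Section 6 describes registration and does not say that slide features enter the fusion. Section 3's sentence assigns no roles, and pathology is needed in validation anyway, as the reference standard.

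Much of this stands. A reader might infer that the evaluated model definitely takes slides as input and that its AUC is therefore certainly circular. The documents do not support that, because inference-time inputs are nowhere listed. That the label comes from the very same slides is a strong inference from Sections 1 and 5, not a statement. Leakage of pathology-derived location is a possibility that the text leaves open; Section 6 can equally mean lesions already identified on imaging.

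The reply does not remove the point. No section states the training-only reading, while Sections 2 and 3, taken at their wording, permit the circular one. Nor is this a detail to leave to an analysis plan: the inputs from which the AUC is computed define the primary outcome.

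**Conclusion.** The concern holds in a conditional form. Followed as worded, the protocol can produce a primary AUC in which slides are both predictor and source of the label. Such an AUC could not support the pre-biopsy claim. The protocol contradicts its own purpose here, and nothing in it settles the matter.

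The size runs from zero (slides confined to training) to near-complete dominance by the slide. In the illustration with slide AUC 0.97, the fused AUC is 0.970 to 0.980 whatever imaging contributes between 0.50 and 0.80. Those figures rest on assumed AUCs, binormal scores and conditional independence, and they apply only if slides are an input at evaluation. They are not estimates for this study. Because the ambiguity sits in the primary objective and outcome, it should be corrected before the model is evaluated.

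**What to change.** Amend Sections 2, 6 and 7, and bring Section 3 into line:

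- **Primary outcome:** the AUC, in held-out patients and external cohorts, of the model run only on inputs available before biopsy. These are mpMRI and TRUS, with or without the clinical variables already collected (age, BMI, PSA indicators, PI-RADS). State which of these clinical variables are used.
- **Role of slides:** registration, labelling or supervision in training only. No slides, and no pathology-derived masks or coordinates, go to the model in any validation fold or cohort.
- **Label:** state how csPCa is defined from the pathology grade, and name the specimen (biopsy or prostatectomy) that supplies it.
- **Slide-based models:** report any of these separately as a pathology-grading analysis, not as non-invasive prediction.

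**Cost.** If imaging-only inference is already intended, this takes a few sentences. If not, an imaging-only inference path must be built and the evaluated model changes. Neither case needs new patients or data. The AUC may be lower, but it will answer the question that the study asks.

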## 5. DATA COLLECTION

Collected clinical data include age, BMI, PSA-related serological indicators and PI-RADS v2.1 scoring results. Imaging data cover preoperative mpMRI and TRUS images. Pathological data include digital whole-slide images of prostate biopsy or radical prostatectomy specimens, corresponding Gleason score and ISUP grading results. All data are fully de-identified to guarantee participant privacy and data security.

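### Secondary objective 4 sets out to verify value in reducing biopsies and overtreatment, but the design supports only a hypothetical projection of biopsies avoided, and nothing on overtreatment

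*Protocol*

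**What the plan says.** Protocol section 2 (Study Objectives) gives the fourth secondary objective as "To verify the clinical value of the model in optimizing prostate biopsy strategies, reducing unnecessary puncture and overtreatment", followed by better early diagnosis and risk stratification. The third secondary objective, listed separately, already covers net benefit through decision and clinical impact curves, and section 6 repeats that analysis.

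Section 3 (Study Design) describes the study in these terms:
- Type: "This is a prospective and retrospective multicenter observational cohort study".
- Use of the model in care: "No additional clinical interventions, experimental drugs or medical devices are applied to enrolled participants".
- Procedures: imaging is "followed by clinically indicated prostate biopsy or radical prostatectomy with definitive pathological diagnosis".
- Scope of data: "Only routine standard-of-care clinical data, imaging data and pathological data are collected and analyzed".

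Section 5 (Data Collection) states: "Collected clinical data include age, BMI, PSA-related serological indicators and PI-RADS v2.1 scoring results". It adds the mpMRI and TRUS images, the "digital whole-slide images of prostate biopsy or radical prostatectomy specimens", and Gleason and ISUP results. Section 7 (Outcome Measures) contains one outcome: "AUC of the multimodal deep learning model for predicting clinically significant prostate cancer at the time of baseline imaging and pathological data collection".

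**The concern.** Reducing biopsies and overtreatment is an effect on care. To verify such an effect, the model's output has to reach a decision, the decision has to be able to go either way, and what follows has to be recorded. The protocol provides for none of these.

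As worded, objective 4 invites the study to present a good AUC and a favourable decision curve as evidence that the model reduces biopsies and overtreatment. The design does not support that conclusion. The objective also names only a benefit. Any rule that spares biopsies does so at some cost in missed clinically significant cancer (csPCa), and neither side of that trade-off is listed as an outcome in section 7.

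Sampling is not the issue here. A perfectly representative cohort under this design could not show an effect on care either.

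**Working it through.** The protocol gives no figure for this objective, so there is nothing to reproduce. The check is mainly a comparison of what the objective needs with what the plan provides.

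**1. Does the model influence care?** Section 3 applies nothing to participants. No section has model output shown to a clinician, and there is no model-guided arm, period or comparator. The number of men whose care the model changes is 0 of the planned 3000.

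**2. Can the number of procedures vary with the model?** Section 4 admits men scheduled for, or having had, biopsy or prostatectomy, and requires complete pathology. Every analysed man therefore has the procedure, so the observed reduction attributable to the model is zero by construction.

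**3. Are the consequences recorded?** The listed data are age, BMI, PSA indicators, PI-RADS, images, slides, Gleason and ISUP. No treatment decision, surveillance status or later outcome is listed. Specimen type shows that a prostatectomy took place, not that it was excessive.

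**4. Does follow-up help?** The title page gives a target follow-up of 12 years, but no follow-up variable or outcome is attached to it. The stated study dates run only from May 30, 2025 to December 31, 2030.

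**5. What can be estimated?** Each biopsied man will have a prediction and a pathology result. At a given threshold, one can count the men without csPCa who would have fallen below it (unnecessary biopsies avoided) and the men with csPCa who would have fallen below it (cancers missed). This is a projection under an assumed policy, and it applies to men who were biopsied.

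**6. Illustration of the trade-off.** The inputs are all assumptions, none from the protocol: equal-variance binormal scores, AUC 0.80 to 0.90, a cut-off giving 95% sensitivity, and csPCa prevalence of 30% or 40%.

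- Separation: d = √2 × Φ⁻¹(AUC). Specificity at 95% sensitivity = Φ(d − 1.645).
- AUC 0.80: d = 1.190, specificity = Φ(−0.455) = 0.3247.
- AUC 0.90: d = 1.812, specificity = Φ(0.167) = 0.5665.
- Unnecessary biopsies avoided per 1000 = 1000 × specificity × (1 − prevalence).
- csPCa missed per 1000 = 1000 × 0.05 × prevalence.

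| Assumed prevalence | Avoided, AUC 0.80 | Avoided, AUC 0.90 | csPCa missed |
|---|---|---|---|
| 30% | 0.3247 × 700 = 227 | 0.5665 × 700 = 397 | 50 × 0.30 = 15 |
| 40% | 0.3247 × 600 = 195 | 0.5665 × 600 = 340 | 50 × 0.40 = 20 |

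All biopsies avoided, missed cancers included, would be 242 to 412 at 30% prevalence and 215 to 360 at 40%. The avoided column in the table is the one that matches the objective's own term, unnecessary biopsy.

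**The case against.** The strongest defence is that the object of *verify* is clinical value, not an observed reduction. Read beside the third objective and section 6, objective 4 may mean only the potential value projected by the planned curves. A clinical impact curve shows, across thresholds, how many men are flagged as high risk and how many of those have csPCa. With prevalence, that yields biopsies avoided and cancers missed. This stands in part: the biopsy component can legitimately be projected, and the planned analyses go most of the way. It does not save the wording. Objective 4 is listed apart from the objective that covers the curves, and a projection supports *estimate*, not *verify*.

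A second defence is that the data hold some treatment information. A reader might infer from the list in section 5 that none is collected; that goes too far. Specimen type identifies men with a prostatectomy specimen, and those among them without csPCa on pathology would be a crude group to count. Section 5 also says that the clinical data *include* the listed items, so the list may not be exhaustive. But the count would cover surgery only and would not establish overtreatment, which the protocol does not define.

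A third defence is that thresholds and intervals belong in a statistical analysis plan not seen here. That is fair for those details. It does not answer the main point, because an analysis plan cannot create model-guided care that did not occur.

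Finally, the matter concerns one secondary objective, and the illustrative counts do not measure the defect. Both remarks are correct.

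**Conclusion.** The point holds in this form: the study cannot show an actual reduction in biopsies or overtreatment. For biopsies it can support a hypothetical projection among biopsied men. For overtreatment there is no definition, no stated analysis and no listed variable that would show whether treatment was excessive.

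Two stronger readings are not supported. One is that nothing at all can be said about biopsies; the planned decision and clinical impact curves contradict this. The other is that the study will report a verified reduction; the protocol does not say how results will be worded, only that the objective invites such a claim.

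The size of the problem is structural and rests on no numerical assumption: no participant's care depends on the model. The illustrative 195 to 397 unnecessary biopsies avoided, against 15 to 20 csPCa missed per 1000, rests wholly on the assumed AUC, prevalence, cut-off and score distribution. It shows only that benefit and harm must be reported together. The primary objective and its AUC analysis are unaffected, so this should be corrected but does not threaten the main result.

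**What to change.** Reword objective 4 along these lines: to estimate, in biopsy-referred men in the held-out validation data, the number of men without csPCa whose biopsy would potentially be avoided and the number of csPCa that would be missed, per 1000 men, each with a 95% confidence interval, at an analysis threshold fixed on development data before the validation data are opened. This threshold serves the analysis only and sets no clinical rule.

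List the two counts as a secondary outcome in section 7 and report them alongside the planned curves. Delete overtreatment from the objective, and leave it and any real-world effect on care to a later impact study in which the model guides decisions and treatment is recorded.

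The cost is a protocol amendment and one table from data already planned. The downside is a more modest claim. Recruitment is under way, so the change should be made before validation results are seen.
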